#### 10.5.1 Primary Analysis

NOTE: The following description for the primary analysis was prepared to implement the intention of the protocol, however in view of the early stopping of the trial this analysis will not be performed, unless the simple summary statistics suggest a finding of interest, in which case this would be performed as an exploratory analysis.

The primary analysis will use a mixed model with repeated measures (MMRM) to compare the GST score between ATH-1017 and placebo at 26 weeks. In this MMRM model, GST score (a composite of the standardized change from baseline variables) will be considered as the outcome variable and the following fixed terms: baseline value, treatment arm, visit, treatment by visit interaction, baseline by visit by treatment interaction, GBA genotype, and baseline age. The correlations among repeated observations within a patient will be accounted for by specifying an unstructured covariance matrix. The least squares mean, and treatment differences will be estimated from the MMRM model.

The MMRM model summary will contains LSMEAN, Standard Error (SE), 95% CI at each visit by treatment (ATH-1017, Placebo) will be displayed. Also, LSMEAN for ATH-1017 difference from placebo, SE, 95% CI, and p-value at Week 26.

If convergence not met for the MMRM model, GST score between ATH-1017 and placebo at Week 26 will be compared using one sided t-test 2.5% significance level.

Additionally, the GST score will be listed and summarized for all visits. This summary will be produced for each disease type and AChEI usage within disease type also. A line plot with mean GST score and 95% CI over visit by treatment arm (40 mg ATH-1017, 70 mg ATH-1017 and placebo) will be displayed.

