#### 6.1 Study Design

This is a Phase 2 multicenter, randomized, double-blind, placebo-controlled, parallel-group, dose ranging study comparing ATH-1017 40 mg/day and ATH-1017 70 mg/day with placebo in subjects with a clinical diagnosis of PDD or DLB (Postuma et al, 2015; Emre, 2007; McKeith, 2017), and with a Montreal Cognitive Assessment (MOCA) score of 11 to 23 at Screening (see Figure 1 for a diagram of the study schema). The study will be conducted at a total of approximately 15 centers in the USA. Subjects and their caregivers will be required to sign an informed consent form (ICF) and will be evaluated against the inclusion/exclusion criteria during a screening period; all eligible subjects will have the option to be tested for glucocerebrosidase (GBA) genotype. Subjects who meet all inclusion/exclusion criteria will undergo baseline ERP P300 assessments at 2 separate baseline visits. At the first baseline assessment (Visit 2a, Prebaseline, Day-10 to Day-3), ERP P300 data shall be uploaded for quality check immediately after completion of the visit. At the second baseline visit (Visit 2b, Baseline, Day 1), no more than 10 days after the Pre-baseline visit, eligible subjects will be randomized in a ratio of 1:1:1 to receive ATH-1017 40 mg/day, ATH-1017 70 mg/day, or placebo. At this Baseline visit (Visit 2b), subjects will undergo pre-dose baseline and post-dose ERP P300.

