#### 6.6 Genotyping

Blood sample(s) will be collected at Screening for analysis of GBA genotype in subjects who consented to genotyping.

Confidential Page 27 of 57

Confidential Page 28 of 57

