## 7.1.2 Modified Intent-to-Treat (mITT) Population

The modified intent-to-treat (mITT) population will include all randomized subjects who took at least one dose of the study medication and who completed both an ADAS-Cog13 and ERP P300 assessment at Baseline and during at least one post-baseline visit. Subjects will be analyzed according to the dose they were randomized to.

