# 10.5 Efficacy

Summary statistics will include change from baseline comparison of ATH-1017 with placebo using a two-sample t-test without baseline adjustment. All statistical tests will be carried out using a one-sided 2.5% significance level and all comparisons will be reported with 95% confidence intervals for mITT population unless otherwise stated. The comparison between ATH-1017 (40 mg and 70 mg pooled) and placebo will serve as the primary efficacy comparison. This summary will be produced for each disease type and AChEI usage within disease type also.

Confidential Page 35 of 57

No adjustments will be made for multiple comparisons.

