## 10.5.2 Secondary Analysis

NOTE: The following description for the secondary analyses was prepared to implement the intention of the protocol, however in view of the early stopping of the trial this analysis will not be performed, unless the simple summary statistics suggest a finding of interest, in which case these would be performed as exploratory analysis.

The separate key secondary variables ADAS-Cog13 and ERP P300 latency will be analyzed using the MMRM model. Change form baseline ADAS-Cog13 score and change form baseline ERP P300 latency will be used as the outcome variable and the following fixed terms: baseline value, treatment arm, visit, treatment by visit interaction, baseline by visit by treatment interaction, GBA genotype, and baseline age. in the MMRM model. Similar summary statistics will be presented that was used for analysis of the primary endpoint. If MMRM model do not converge, active treatment and placebo groups will be compared using one sided t-test 2.5% significance level at Week 26 for change for baseline secondary variables.

Confidential Page 37 of 57

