# **Appendix 4.** Summary of Efficacy Analyses

**Table 6.** Analyses of Efficacy Parameters

Parameter	Population	Statistical Method	Missing Data	Interpretation	Table Number
GST Score	mITT	t-test/MMRM	NA	Primary analysis	Table 14.2.3.1
CFB ADAS- Cog13 score	mITT	t-test/MMRM	NA	Secondary analysis	Table 14.2.3.2
CFB ERP P300 latency	mITT	t-test/MMRM	NA	Secondary analysis	Table 14.2.3.3

mITT = Modified intent-to-treat; MMRM = Mixed Model Repeated Measures; CFB = change from baseline

Confidential Page 52 of 57

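### Does a GBA genotype term, with genotyping by consent only, leave the optional MMRMs unable to include every mITT subject?

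*SAP*

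**What the plan says.** The MMRM for the GST score (SAP 10.5.1) has these fixed terms: "baseline value, treatment arm, visit, treatment by visit interaction, baseline by visit by treatment interaction, GBA genotype, and baseline age". The models for ADAS-Cog13 and P300 latency (SAP 10.5.2) end with the same ones: "baseline by visit by treatment interaction, GBA genotype, and baseline age. in the MMRM model". Protocol 8.3.1 is the source of the GBA term; it also names site, which the SAP list leaves out.

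Genotyping is voluntary. SAP 6.1 states that "all eligible subjects will have the option to be tested for glucocerebrosidase (GBA) genotype", and SAP 6.6 limits the blood sample to "analysis of GBA genotype in subjects who consented to genotyping". The mITT definition (SAP 7.1.2) asks for a dose, and for an ADAS-Cog13 and "ERP P300 assessment at Baseline and during at least one post-baseline visit". It does not ask for a genotype. The first row of Table 6 in SAP Appendix 4 reads "GST Score mITT t-test/MMRM NA Primary analysis", where NA is the missing-data entry; the other two endpoints have the same entry.

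The status of these models matters as much as their terms. The note that opens SAP 10.5.1 says that "this analysis will not be performed, unless the simple summary statistics suggest a finding of interest", and that it would then be exploratory. SAP 10.5.2 carries the same note. SAP 10.5.6 makes everything beyond summary statistics optional, and SAP section 8 rules out a statistical conclusion from any test that is produced. The comparison that accompanies the summaries (SAP 10.5) is made "using a two-sample t-test without baseline adjustment".

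**The concern.** A model cannot use a subject who has no value for one of its terms unless someone decides how to code that value. The plan puts a voluntary genetic test into the model, assigns the model to mITT, and says nothing about mITT subjects who were not tested. Standard mixed-model software drops records with a missing covariate. An estimate labelled mITT could then rest on fewer subjects than mITT contains, in a trial that SAP 9.5 and 10.5.1.1 already describe as small.

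Three things would be at stake: precision, the match between the label and the subjects analysed, and bias if the untested subjects differed between arms. Protocol 7.4.2 gives the last of these some colour. A subject who withdraws may ask for untested samples to be destroyed, so a result could in principle be lost after randomization.

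**Working it through.** **No plan figure to reproduce.** The sample size is 75 (25 per arm), chosen empirically (SAP 6.1.2), with no effect size, SD or power. The documents give neither the enrolled number nor the share without a GBA result. Every size below rests on an assumed untested share *u*.

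**Which analyses use GBA?**

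| Analysis | Status after the early stop | Uses GBA? |
|---|---|---|
| Two-sample t-test (SAP 10.5) | Default, with the summaries | No |
| GST MMRM (10.5.1) | Only if the summaries suggest interest; exploratory | Yes |
| ADAS-Cog13 and P300 MMRMs (10.5.2) | Same | Yes |
| t-test on non-convergence (10.5.1, 10.5.2) | Fallback for the MMRMs | No |

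**Precision if untested subjects are dropped.** Subjects left = 75 × (1 − u); standard error multiplier = 1/√(1 − u).

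| u (assumed) | Subjects left | SE multiplier |
|---|---|---|
| 0% | 75 | 1.00 |
| 10% | 67.5 | 1.05 |
| 20% | 60 | 1.12 |
| 30% | 52.5 | 1.20 |
| 40% | 45 | 1.29 |

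**Simulation check.** This used a one-visit linear model, not the full MMRM, with 20,000 runs per cell. Assumptions: residual SD 1, no true effect, 20% carriers shifted by 0.5 SD, untested subjects shifted by 0.3 SD, missingness unrelated to arm. The contrast is pooled ATH-1017 against placebo, as in SAP 10.5, so 50 v 25 at planned size. With nobody untested, √(1/50 + 1/25) = √0.06 = 0.245, and the simulation gives 0.245. Complete-case standard errors at 0/10/20/30/40% untested are 0.245/0.259/0.275/0.296/0.324, and 0.324/0.245 = 1.32, close to the simple formula. At assumed smaller sizes, 0% and 40% untested give 0.414 and 0.571 (18 v 9), and 0.516 and 0.717 (12 v 6).

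**What the two sensible ways of filling the gap give**, at 20% untested:

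| Size | Complete case | Untested as own level | No GBA term | Ratio of the last two |
|---|---|---|---|---|
| 50 v 25 | 0.275 | 0.247 | 0.250 | 0.99 |
| 18 v 9 | 0.473 | 0.426 | 0.417 | 1.02 |
| 12 v 6 | 0.593 | 0.537 | 0.513 | 1.05 |

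Both keep all subjects and avoid most of the loss. The gap between them is 1% to 5% and depends on the assumed carrier share and effect.

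**Bias.** With 30% of active and 10% of placebo subjects untested, but no link to outcome, the mean estimates at 50 v 25 (8,000 runs, true value 0) were −0.004 (complete case), −0.003 (own level) and −0.003 (no term). Dependence on arm alone therefore does not shift the contrast. With an added correlation of 0.3 between being untested and the outcome, they were −0.092, −0.103 and −0.002. Both links are needed.

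**Can both links arise here?** GBA consent and blood sampling take place at Screening (Protocol 6.6 and Table 1; SAP 6.6), before randomization, so declining the test cannot depend on arm. The one later route is destruction of an untested sample on withdrawal. Protocol 7.4.1 withdraws subjects who permanently stop treatment, so many of them would have no Week 26 value however GBA is handled. The simulation gives every such subject an outcome, and so flatters the model without GBA in that scenario.

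**The case for a change.** The best argument for a change concerns timing. The MMRM is fitted only after the summaries have suggested something of interest, so the choice between dropping, coding or ignoring untested subjects would be made with comparative results in view. One sentence written beforehand would remove that freedom at almost no cost. Nor does the fallback t-test help, because it applies only when the model fails to converge, and a complete-case model can converge on too few subjects. The clause in SAP section 8 that permits other comparison tests is not a rule for a missing covariate.

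All of that is true as description. The silence is real, and a report of such a model should give the number of subjects in it. The argument has less force as a reason to amend the plan. Whether to fit the model at all is already decided after the summaries are seen, so a rule for one covariate would not make the result confirmatory, and the SAP already forbids a conclusion from it. The loss of subjects would not be wholly hidden either: SAP 10.2 summarises baseline GBA genotype by treatment, although for the safety population and not as a model count.

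The silence may also be only apparent. The public SAP is redacted, sections 10.5.3 and 10.5.4 are not shown, and the reference list holds a missing-data paper that no readable text cites. The NA in Table 6 may mean only that nothing is imputed.

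**Conclusion.** The gap exists and is a missing detail of the ordinary kind. GBA is a listed term, testing is by consent, and the readable text does not say how an untested mITT subject enters the model. It affects a result only if the optional model is run, at least one mITT subject has no genotype, and the analyst lets the software drop that subject.

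Even then the cost is precision in an exploratory estimate: nothing at 0% untested, about 12% on the standard error at an assumed 20%, and 29% to 39% at an assumed 40%, depending on the formula or simulated size used. Nothing in the plan tells the analyst to exclude anyone, and either common remedy avoids most of the loss. Which remedy to prefer is a matter of taste at these sizes. Bias would need missing results related to both arm and outcome, for which the documents give no evidence.

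The default t-test is untouched and no conclusion may be drawn from the models, so no change to the plan follows. This rests on the models keeping the exploratory status that the SAP gives them; all magnitudes rest on the assumed untested shares, carrier share and effect sizes.

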# 4.1 Number of Subjects

The study will randomize approximately 75 subjects in a 1:1:1 ratio to ATH-1017 40 mg, ATH-1017 70 mg, and placebo groups.

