#### 5.4.2 Randomization Numbers

Prior to dosing on Day 1, subjects will be assigned a randomization number generated by an IRT system; the randomization numbers will subsequently be incorporated into the Electronic Data Capture (EDC) system.

Once a randomization number has been allocated to 1 subject, it may not be assigned to another subject.

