### 8.3 Clinical Effect Analyses

## 8.3.1 Primary Clinical Effect Analysis - GST

The primary hypothesis is that treatment with ATH-1017 will result in a statistically significant reduction in change from baseline in the GST score (O'Brien, 1984) (combining the ADAS-Cog13 score and the change from baseline in ERP P300 at Week 26) relative to the placebo group in the mITT population. The primary analysis will test the statistical hypothesis of no difference between placebo and 70 mg ATH-1017 first and then 40 mg ATH-1017 versus placebo.

The primary analysis will use a mixed model with repeated measures (MMRM) to compare the estimated change from baseline between active treatment and placebo in the GST score. This analysis will assess whether or not there is a difference in estimated GST values between treatment groups and placebo at 26 weeks using least squares means estimates from the MMRM model, and will include terms for baseline, baseline by time interaction, and baseline by time by treatment interaction in the model. Additional terms will be included for GBA genotype, and site (with smaller sites grouped), and age. Least squares means and standard errors will be estimated from the MMRM model at Week 26. Further details relating to the primary analysis will be described in the SAP.

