#### 9 OVERALL STATISTICAL CONSIDERATIONS

#### 9.1 General Conventions

Efficacy and safety data will be summarized and presented by disease type (PDD or DLB), acetylcholinesterase inhibitor (AChEI) usage within disease type, treatment group, and time point in summary tables. Continuous variables will be presented by descriptive statistics: n, mean, standard deviation (SD), median, minimum, and maximum. Categorical variables will be tabulated by frequency count and percentage. Percentages are based on the number of subjects in each treatment group in the given population for AE summary tables, and additionally overall for medical history, prior and concomitant medications. For all other tables, percentages are based on the number of subjects with non-missing data in each treatment group and overall for the given population.

Means, medians and percentiles will be displayed to one more decimal place than the data, dispersion statistics (e.g., standard deviation) will have two more decimal places, and the minimum and maximum will be displayed to the same number of decimal places as reported in the raw data. Percentages will be displayed with one decimal place. P-values will be quoted to 4 decimal places consistent with SAS PVALUEw.d format set to PVALUE6.4. P-values < 0.0001 will be presented as p<0.0001.

Listings will include all subjects with defined analysis population for each listing. Listings will generally be sorted by disease type, treatment, subject ID, parameter and visit date/study day. Unscheduled visits will also be included in the listings.

Days will be converted to weeks by dividing by seven. Days will be converted to months by dividing by 30.44. Days will be converted to years by dividing by 365.25. All data collected during the study will be analyzed and reported except as stated otherwise.

All data will be analyzed using the SAS® Version 9.4 or later.

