#### **10.6.1** Adverse Events

All adverse events will be coded using the most current version of the Medical Dictionary for Regulatory Activities (MedDRA). A treatment-emergent adverse event (TEAE) is defined as any adverse event that begins or worsens in severity on or after the first study drug dose date until follow-up period. Treatment Related AE includes probably related, possibly related or related AEs. Injection Site Reactions will be identified from high level term (HLT) as 'Injection Site Reactions'.

The number and percentage of subjects experiencing one or more adverse events in the following adverse event categories will be summarized for each treatment group, and overall. No comparisons of treatment groups will be performed.

- Any AE
- Any TEAE
- Any Treatment Related TEAE (possibly related; probably related; related)
- Any severe TEAE

Confidential Page 38 of 57

- Any serious TEAE
- Any TEAE that led to discontinuation of study drug
- Any fatal TEAE
- All deaths

Treatment emergent adverse event (TEAE) incidence will be summarized and presented using primary MedDRA system organ classes (SOCs), and preferred terms (PTs).

- All TEAE
- Any Treatment Related-TEAE
- Study Drug Related Treatment-Emergent Adverse Events by Worst Severity
- Any serious TEAE by Worst Severity
- Any TEAE that led to discontinuation of study drug
- Treatment-Emergent Adverse Events Leading to Death
- Injection Site Reactions Treatment-Emergent Adverse Events

The following listings of adverse events will be prepared.

- All adverse events
- Drug Related Treatment-Emergent Adverse Events
- Injection Site Reactions Treatment-Emergent Adverse Events
- Serious Treatment-Emergent Adverse Events
- Treatment-Emergent Adverse Events Leading to Study Discontinuation
- Death listing

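### The overall ATH-1017 versus placebo comparison adjusts for neither disease type nor AChEI use, the two factors by which the SAP splits most of its summaries

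*SAP*

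**What the plan says.** **Splitting.** SAP 9.1 sets the general rule: "Efficacy and safety data will be summarized and presented by disease type (PDD or DLB), acetylcholinesterase inhibitor (AChEI) usage within disease type", then treatment group and time point. SAP 10.1 to 10.4, 10.5, 10.5.1, 10.6.6 and 10.6.7 repeat it. For the efficacy t-tests, SAP 10.5 adds: "This summary will be produced for each disease type and AChEI usage within disease type also". Not every section restates the split. The adverse event categories in SAP 10.6.1 "will be summarized for each treatment group, and overall", and the laboratory, ECG and vital-sign sections likewise name only treatment group.

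**Randomization.** Protocol 4.1: "The study will randomize approximately 75 subjects in a 1:1:1 ratio". Protocol 5.4.2: "subjects will be assigned a randomization number generated by an IRT system". No stratification factor is described in either document.

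**Comparison in force.** SAP 10.5 compares pooled 40 mg and 70 mg with placebo by a two-sample t-test that has no baseline adjustment, one-sided at 2.5%, with 95% confidence intervals.

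**Mixed models.** Besides baseline score, arm, visit and their interactions, the protocol model (8.3.1) says: "Additional terms will be included for GBA genotype, and site (with smaller sites grouped), and age". The SAP model (10.5.1, same terms in 10.5.2) drops site and keeps "baseline by visit by treatment interaction, GBA genotype, and baseline age". Neither version contains disease type or AChEI use. The SAP model is conditional: "this analysis will not be performed, unless the simple summary statistics suggest a finding of interest", and then it is exploratory. If it does not converge, the fallback is again a t-test.

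**Status and data.** SAP 8 rules out any statistical conclusion from a test. SAP 10.2 tabulates disease type and AChEI use at baseline. Protocol 7.3.2 permits stable AChEI use, so users and non-users can mix in each arm.

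**The concern.** The plan's layout and its estimates do not match. Disease type and AChEI use are important enough to organize most tables, yet the one overall comparison ignores both. The models instead adjust for GBA genotype, which is known only for subjects who consented to genotyping (Protocol 6.6).

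In a small trial with no described stratification, the pooled active group and the placebo group can differ by chance in the share of DLB subjects or AChEI users. If either factor predicts change in ADAS-Cog13 or P300 latency, the overall estimate carries part of that difference. Split tables show the pattern but do not correct the overall figure. The mixed model is run only when the summaries look interesting, which is when a reader most needs to know whether an imbalance explains the result. As specified, it cannot answer that for these two factors.

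**Working it through.** **Inputs from the documents.** 25 per arm, 3 × 25 = 75 (Protocol 8.6; the total reproduces). Pooled contrast: 50 versus 25. One-sided level 0.025 (SAP 10.5). The plan states that no formal sample size calculation was made, so there is no power figure to reproduce.

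**Assumptions, none given in the documents.** Factor prevalence 30% to 50% (70% gives the same results as 30%). Prognostic gap of 0.2, 0.3 or 0.5 SD per factor. The two factors independent. Outcome SD 1. The number enrolled is not given; SAP 9.5 says only that it is smaller, so several sizes are shown.

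**1. Chance of an imbalance of at least 20 points.** With independent binomial counts X_A and X_P, sum the probabilities of all pairs for which |X_A/n_A − X_P/n_P| ≥ 0.20. For at least one of two factors, use 1 − (1 − q)².

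| Pooled active vs placebo | Prevalence 30% | Prevalence 50% | At least one of two factors |
|---|---|---|---|
| 50 vs 25 (planned) | 9.0% | 12.1% | 17.2% to 22.7% |
| 20 vs 10 (assumed) | 32.6% | 36.9% | 54.5% to 60.2% |
| 16 vs 8 (assumed) | 27.2% | 31.6% | 46.9% to 53.2% |
| 10 vs 5 (assumed) | 55.5% | 59.1% | 80.2% to 83.2% |

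The 16 vs 8 row dips because differences there move in steps of 1/16, so the first attainable value at or above 0.20 is 0.25.

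**2. Shift in the estimate.** Shift = imbalance × prognostic gap: 0.20 × 0.2 = 0.04 SD, 0.20 × 0.3 = 0.06 SD, 0.20 × 0.5 = 0.10 SD. At 50 vs 25 the standard error is √(1/50 + 1/25) = 0.245 SD, so the largest shift is 0.10/0.245 = 0.41 SE. At 20 vs 10 the standard error is √(1/20 + 1/10) = 0.387 SD, and the same shift is 0.26 SE.

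**3. Error rate given that imbalance.** 1 − Φ(1.96 − shift/SE), with the imbalance favouring active:
- 50 vs 25, one factor: 0.036, 0.043 and 0.060 for gaps of 0.2, 0.3 and 0.5 SD.
- 50 vs 25, both factors imbalanced the same way: 0.051, 0.071 and 0.126.
- 20 vs 10, one factor: 0.032 to 0.044.

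**4. Error rate averaged over randomization.** A simulation of 20,000 trials at 50 vs 25, with both factors worth 0.5 SD and an unadjusted t-test, gives 0.0246 against the nominal 0.025. The Monte Carlo standard error is √(0.025 × 0.975/20,000) = 0.0011. The test keeps its level.

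**5. Precision gained by adjusting.** At 50% prevalence, R² = 2 × 0.25 × gap² = 0.02, 0.045 and 0.125. Power at 50 vs 25, one-sided 0.025, with the residual SD reduced to √(1 − R²):
- True effect 0.5 SD: from 0.532 to 0.541, 0.551 and 0.588.
- True effect 0.7 SD: from 0.815 to 0.823, 0.833 and 0.863.

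**6. Size of the split cells.** Even at the planned size and with even splits, four disease-by-AChEI cells hold 75/4 = 18.75 subjects each, or 25/4 = 6.25 per arm.

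**The case against.** The strongest reply is that little depends on these analyses. The mixed models are conditional and exploratory, SAP 10.5.6 makes everything beyond summary statistics optional, and SAP 8 forbids a statistical conclusion. That stands, and it sets the severity.

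Second, a reader might infer that missing adjustment invalidates the test. It does not. Chance imbalance under randomization is already part of the standard error, and step 4 shows the level is kept. Only conditional bias and some lost precision remain.

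Third, the SAP is not silent on imbalance: the baseline table would show it, and the within-stratum summaries compare arms among like subjects. That is a real but weak safeguard, with about 6 per arm per cell at best.

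Fourth, no passage says that either factor predicts the outcome. Protocol 1.1 describes DLB and PDD as sharing the same underlying brain changes. The size of the shift therefore rests on assumption. It remains true that the SAP itself chose these factors to organize its results.

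Fifth, more terms could strain a model that already has an unstructured covariance and a three-way interaction. This is fair, and it is a reason to have a simpler adjusted analysis ready.

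**Conclusion.** The point holds as a minor one. Neither document as supplied describes stratification by disease type or AChEI use, and no specified overall comparison adjusts for them. At the planned size there is a 9% to 12% chance of a 20-point imbalance in a given factor. At an assumed 20 versus 10 the chance is 33% to 37%. The resulting shift is 0.04 to 0.10 SD per factor, which is less than half a standard error in every case shown. These figures depend on the assumed prevalence, prognostic gap and enrolled number.

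Three stronger readings go beyond the documents:
- That every result is split. Several safety sections name treatment group only, although the general convention in SAP 9.1 would reach them, and the mixed-model estimate is not specified by stratum.
- That randomization was certainly unstratified. Strata could stand in IRT specifications or text not supplied; the documents show only that none is described.
- That an adjusted estimate should replace the t-test as the main result. The SAP deliberately limits itself to minimal analyses, so a supportive estimate is enough.

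**What to change.** 1. In SAP 10.5, beside the overall Week 26 t-test, report a supportive linear-model estimate of pooled ATH-1017 versus placebo with its 95% confidence interval, adjusted for disease type (PDD/DLB) and baseline AChEI use (yes/no).
2. In SAP 10.5.1 and 10.5.2, add the same two main effects to the mixed models if they are run. Name the adjusted linear model as the fallback if a model does not converge.
3. Keep the split tables, labelled as descriptive.

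Both factors are already planned for the baseline table, so no new data are needed. The cost is a short SAP change, one extra estimate per endpoint, 2 degrees of freedom and a small added risk of non-convergence in the mixed models. At an assumed 20 versus 10, error degrees of freedom fall from 30 − 2 = 28 to 30 − 4 = 26. Stratification itself cannot be added after randomization. If the enrolled number cannot support the two terms, the SAP should say so.

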#### 7.4.1 Discontinuation of Study Treatment

All subjects who permanently discontinue study treatment, for whatever reason, will be withdrawn from the study. Upon discontinuation of study drug, subjects will continue with their original treatment; tapering off study medication is not required.

See the schedule of activities for data to be collected at the time of treatment discontinuation and follow-up and for any further evaluations that need to be completed (Table 1).

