#### 6 STUDY DESIGN CONSIDERATIONS

This study (ATH-1017-PD-0201) is designed to demonstrate as a safety and proof of concept study of ATH-1017 in PDD and DLB subjects. Eligible participants will receive once daily (OD) subcutaneous (SC) injections of ATH-1017 (40 mg or 70 mg) or placebo, over a 26-week double-blind period, followed by a 4-week safety follow-up.

NOTE: This study was stopped early; safety listings and summaries will be performed as previously envisioned; however efficacy and biomarker analyses will be exploratory in nature.

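### If the exploratory MMRM does not converge, the SAP goes straight to a Week 26 t-test that ignores earlier visits and largely repeats the default comparison

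*SAP*

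**What the plan says.** **The model and its fallback.** SAP 10.5.1 fits an MMRM to the GST score, in which within-subject correlation "will be accounted for by specifying an unstructured covariance matrix". No second structure is listed. The only instruction for failure is: "If convergence not met for the MMRM model, GST score between ATH-1017 and placebo at Week 26 will be compared using one sided t-test", at the 2.5% level. SAP 10.5.2 repeats this for ADAS-Cog13 and P300 latency: "If MMRM model do not converge, active treatment and placebo groups will be compared using one sided t-test 2.5% significance level at Week 26". SAP Appendix 4, Table 6 enters NA under missing data for all three endpoints. Protocol 8.3.1 plans the MMRM and names no fallback test.

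**Status of the model.** SAP 6 records that "This study was stopped early; safety listings and summaries will be performed as previously envisioned" and makes efficacy analyses exploratory. The note opening SAP 10.5.1 says that "this analysis will not be performed, unless the simple summary statistics suggest a finding of interest"; SAP 10.5.2 carries the same condition. SAP 8 rules out statistical conclusions from any test and permits alternative comparison tests. SAP 10.5.6 makes everything beyond summary statistics optional. SAP 10.5 already compares ATH-1017 with placebo "using a two-sample t-test without baseline adjustment".

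**Who has a Week 26 value.** SAP 9.6 assigns early-termination visits by study day and sets Week 26 as Days 162-196. Protocol 7.4.1 states: "All subjects who permanently discontinue study treatment, for whatever reason, will be withdrawn from the study". Protocol 7.4.2 nevertheless asks sites to try to bring early discontinuers back for Visit 8 at Week 26.

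**The concern.** The MMRM likelihood uses the Week 2 and Week 12 values of a subject with no Week 26 value. The fallback uses none of them. The step therefore replaces an analysis that is valid when loss depends on observed earlier scores with one that needs the subjects left at Week 26 to be comparable between arms. Adding a baseline covariate to the t-test would not restore the missing subjects.

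The trigger makes this worse. The MMRM is run only if the simple summaries look interesting, and those summaries include the unadjusted t-test. If the model then fails, the SAP returns to essentially that same comparison, and nothing has tested it.

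Non-convergence is most likely where few Week 26 values exist, which is also where the available-case comparison is weakest. The stake is how an apparent exploratory signal, reported with an estimate and a 95% interval, is read.

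**Working it through.** **1. Who is lost.** Under SAP 9.6 a subject last assessed on Day 100 falls in the Week 12 window (Days 64-112). That subject contributes to the MMRM but not to the Week 26 t-test. A subject seen in Days 162-196, whether at an early-termination or a return visit, is kept.

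**2. How heavy the model is.** Assume two pooled arms and a binary GBA term. GST has three visits (Weeks 2, 12, 26). Fixed effects are: intercept 1 + treatment 1 + visit 2 + treatment-by-visit 2 + baseline 1 + baseline-by-visit-by-treatment 5 + GBA 1 + age 1 = 14. Unstructured covariance adds 3 × 4 / 2 = 6. For ADAS-Cog13 (four visits) the counts are 1 + 1 + 3 + 3 + 1 + 7 + 1 + 1 = 18, plus 4 × 5 / 2 = 10. SAP 9.5 and 10.5.1.1 describe enrolment as small but give no number, so non-convergence is a realistic risk that cannot be quantified.

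**3. The plan's own figure.** The planned sample is 3 × 25 = 75. SAP 6.1.2 gives no effect size, SD, power or dropout rate, so there is nothing further to reproduce.

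**4. Bias.** Simulation, 1,500 trials per setting. Assumptions:
- 25 placebo and 50 active (planned numbers); GST at Weeks 2, 12 and 26 with unit SD.
- Adjacent-visit correlation 0.5 or 0.7; true Week 26 effect 0 or -0.5 SD, lower being better.
- Response-related stopping driven by the last observed score, set to lose about 20% or 40% by Week 26. Where only one arm stops this way, the other loses about 10% or 28% at random.
- No discontinuer returns at Week 26.

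Bias of the Week 26 available-case difference, in SD (negative favours active; Monte Carlo error about 0.25-0.32 / √1500 = 0.006-0.008):

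| Stopping pattern | True effect 0 | True effect -0.5 |
|---|---|---|
| Poor response, same rule in both arms | -0.01 to 0.00 | +0.01 to +0.04 |
| Poor response, placebo only | +0.10 to +0.27 | +0.10 to +0.28 |
| Poor response, active only | -0.10 to -0.27 | -0.08 to -0.25 |
| Unrelated to response | not run | 0.00 to +0.02 (noise) |

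On the same data, unstructured maximum likelihood was within 0.015 SD of the truth throughout. Generalised least squares on all visits, with a compound-symmetric covariance whose correlation was fixed at the true average, was within 0.02 SD.

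**5. Precision.** With loss unrelated to response, the ratio of t-test variance to likelihood variance was:
- correlation 0.5: (0.269/0.265)² = 1.03 at 20% loss, (0.313/0.307)² = 1.04 at 40%;
- correlation 0.7: (0.273/0.258)² = 1.12 at 20% loss, (0.317/0.293)² = 1.17 at 40%.

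For context, power at 0.5 SD and one-sided 2.5% is Φ(0.5/√(1/n₀ + 1/n₁) - 1.96):
- 25 vs 50: Φ(2.041 - 1.96) = 53%;
- 20 vs 40: Φ(1.826 - 1.96) = 45%;
- 15 vs 30: Φ(1.581 - 1.96) = 35%.

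Most of that fall comes from losing subjects. The model would recover only the modest part shown by the variance ratios.

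**The case against.** The strongest reply is that little hangs on this. The MMRM is not run by default, it is exploratory if run, and SAP 8 bars conclusions from it. A t-test is already the main comparison, so dependence on available Week 26 data does not begin with non-convergence. SAP 8 also allows alternative tests. All of this stands and limits the impact. It does not remove the point: permission to choose another test later is not a pre-specified choice, and estimates with intervals will still be reported. It does mean that a change confined to 10.5.1 and 10.5.2 would leave the same unlabelled comparison in 10.5.

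A reader might infer that everyone who stopped early is discarded. The documents do not support that. Protocol 7.4.2 seeks a return visit, and SAP 9.6 keeps anyone assessed in Days 162-196.

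A reader might also infer that stopping after poor response inflates the drug effect. That requires such stopping mainly in the active arms. The withdrawal reasons in Protocol 7.4.2 apply to all arms, and with the same rule in both the bias was at most about 0.04 SD.

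Nor is the MMRM certain to use all of mITT. It includes GBA genotype, testing is optional, and no missing-genotype category is stated, so untested subjects may drop out of the model while the t-test keeps them.

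Finally, a simpler covariance with ordinary sandwich errors has its own cost. In a null simulation (2,000 runs, compound-symmetric working covariance, random Week 26 loss of 20-40%, assumed sample sizes), the uncorrected sandwich with a normal reference gave one-sided error of 3.8-4.5% at 20 vs 10 and 5.1-5.7% at 14 vs 7. With a t reference it was 3.0-4.5%. The t-test gave 2.1-2.8%, against a nominal 2.5%. This stands, and the fix below allows for it.

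**Conclusion.** The point holds in limited form. If the exploratory MMRM is run and fails to converge, the stated rule discards the earlier-visit data of subjects without a Week 26 assessment and largely reproduces the comparison that prompted the model. The precision cost relative to the likelihood model is modest: variance about 3% to 17% larger under the assumptions used. Bias is about 0.1 to 0.3 SD, for or against the drug, only if response-related stopping differs between arms. It is small under a common rule and absent if the loss comes solely from the sponsor's closure and is unrelated to response.

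These sizes rest on assumed loss of 20-40%, visit correlation of 0.5-0.7, the planned sample size and no return visits; the documents supply no effect size, correlation or dropout rate. They do not establish that the drug effect would be overstated. The consequence is confined to interpreting exploratory results, but the change is cheap and worth making.

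**What to change.** In SAP 10.5.1 and 10.5.2, replace the fallback with the following:

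*If the unstructured model does not converge, refit the same fixed effects with heterogeneous Toeplitz, then heterogeneous AR(1), then compound symmetry, and use the first that converges. Base inference on Kenward-Roger, or on a bias-corrected sandwich with a t reference; do not use the uncorrected sandwich. If none converges, remove the baseline-by-visit-by-treatment term and repeat the sequence.*

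For three visits the covariance parameters fall from 6 to 5, 4 and 2; for four visits, from 10 to 7, 5 and 2. Dropping the three-way term cuts the fixed effects from 14 to 9 and from 18 to 11.

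Label the Week 26 t-test as an observed-case comparison, both there and in SAP 10.5. Protocol 7.4.1 and 7.4.2 should be reconciled on whether subjects who stop treatment return at Week 26, because that decides who enters the test.

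The cost is a few sentences and a few lines of SAS code. The small downside is reliance on a simpler covariance structure; a wrong one can bias the estimate when loss depends on earlier scores, though compound symmetry stayed within 0.02 SD in the settings simulated.
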